7.1 General Issues

This study is to be conducted according to US and international standards of Good Clinical Practice (FDA Title 21 part 312 and International Conference on Harmonization guidelines), applicable government regulations and Institutional research policies and procedures.

This protocol and any amendments will be submitted to a properly constituted independent Institutional Review Board (IRB) for formal approval of the study conduct. The decision of the IRB concerning the conduct of the study will be made in writing to the investigator and a copy of this decision will be provided to the sponsor before commencement of this study. The investigator should provide a list of IRB members and their affiliations to the Sponsor.

All subjects for this study will be provided a consent form describing this study and providing sufficient information for subjects to make an informed decision about their participation in this study. The consent form will be submitted with the protocol for review and approval by the IRB for the study. The formal consent of a subject, using the IRB-approved consent form, must be obtained before that subject is submitted to any study procedure. This consent form must be signed by the subject or legally acceptable surrogate, and the investigator-designated research professional obtaining the consent.

7.2 Rationale for Subject Selection

The patients to be entered in this protocol have MM which is an almost always incurable disease and therefore these patients have limited life expectancies. Subjects from both genders and all racial/ethnic groups are eligible for this study if they meet the eligibility criteria. To date, there is no information that suggests that differences in disease response would be expected in one group compared to another. It is not considered reasonable to administer a previously uncharacterized cell therapy to pregnant or lactating women. Children do not develop MM. Efforts will be made to extend accrual to a representative population, but in this preliminary study, a balance must be struck between patient safety considerations and limitations on the number of individuals exposed to potentially toxic and/or ineffective treatments on the one hand and the need to explore gender and ethnic aspects of clinical research on the other hand. If differences in outcome that correlate to gender or to ethnic identity are noted, accrual may be expanded, or a follow-up study may be written to investigate those differences more fully.

7.3 Evaluation of Benefits and Risks

Clinical trial summarized above demonstrated that targeting BCMA in MM by the CAR construct that will be used in the current protocol demonstrated mainly activity-associated toxicity and no off-target or on-target off-tumor effects. Furthermore, as noted above, Descartes-11 is expected to have even a better safety profile than the one used in that trial. Taken together, the potential benefits of the trial outweigh its risks.

7.4 Recordkeeping

7.4.1 Source Data

Source data is all information, original records of clinical findings, observations, or other activities in a clinical trial necessary for the reconstruction and evaluation of the trial. Source data are contained in source documents. Examples of these original documents and data records include hospital records, clinical and office charts, laboratory notes, memoranda, subject diaries or evaluation checklists, pharmacy dispensing records, recorded data from automated instruments, copies or transcriptions certified after verification as being accurate and complete, microfiches, photographic negatives, microfilm or magnetic media, x-rays, subject files, and records kept at the pharmacy, at the laboratories, and at medico-technical departments involved in the clinical trial.

7.4.2 Case Report Forms

The study case report form (CRF) is the primary data collection instrument for the study. All data requested on the CRF must be recorded. All entries will be entered into an electronic data capture system (eCRF). The Principal Investigator is responsible for assuring that the data entered into eCRF is complete, accurate, and that entry and updates are performed in a timely manner.

7.4.3 Confidentiality

The investigator must ensure anonymity of the patients; patients must not be identified by names in any documents submitted to the sponsor. Signed informed consent forms and patient enrollment log must be kept strictly confidential to enable patient identification at the site. Information about study subjects will be kept confidential and managed according to the requirements of the Health Insurance Portability and Accountability Act of 1996 (HIPAA). Those regulations require a signed subject authorization informing the subject of the following:

- What protected health information (PHI) will be collected from subjects in this study
- Who will have access to that information and why
- Who will use or disclose that information
- The rights of a research subject to revoke their authorization for use of their PHI.

If a subject revokes authorization to collect or use PHI, the investigator, by regulation, retains the ability to use all information collected prior to the revocation of subject authorization. For subjects that have revoked authorization to collect or use PHI, attempts should be made to obtain permission to collect at least vital status (i.e., that the subject is alive) at the end of their scheduled study period.

Appendix A MANAGEMENT GUIDELINES FOR CAR T-CELL-RELATED TOXICITIES

The clinical signs and symptoms of CAR T-related toxicities guide the grading and management of CRS and neurotoxicity. This protocol adapts management recommendations described by Lee et al.⁴¹ A copy of this reference will be provided to the investigator and staff are encouraged to review it prior to enrolling the first patient. The following is recommended:

1. All patients with suspicion of CRS or fever above 37.9°C should be admitted for at least a 24-hour observation.
2. Infectious disease work-up with blood cultures should be initiated each time CRS is suspected. Empiric broad-spectrum intravenous antibiotics are recommended.
3. Vital signs should be checked at least every 4 hours with strict urine input and output monitoring.
4. Patients with poor oral intake should be started on intravenous fluids. Patients with 80% of their baseline systolic blood pressure (or if systolic BP<90mmHg) should be given a 0.5-1 L fluid bolus. Fluid boluses can be repeated as needed; however, they should be kept to a minimum with a low threshold of starting low dose vasopressor as the capillary leak during CRS can lead to fluid overload.
5. Patients should be transferred to the Intensive Care Unit (ICU) if:
 - a. the patient's systolic pressure does not respond to the first fluid bolus;
 - b. the patient requires 2 or more fluid boluses within 24 hours;
 - c. the patient's heart rate remains above 125/min for at least 4 hours;
 - d. the patient's supplemental oxygen requirement is more than 40% FiO₂; or
 - e. the patient has >Grade 2 neurotoxicity.
6. Patients admitted to the ICU should have the following:
 - a. vital signs checked every 2 hours;
 - b. cardiac enzymes, ECG and echocardiogram evaluation;
 - c. if systolic blood pressure is below 75% of baseline or below 85 mmHg, norepinephrine should be started;
 - d. CBC should be checked twice a day and cytopenias should be treated as follows:
 - i. blood transfusion to keep Hgb above 8.0 g/dL;
 - ii. platelet transfusion to keep platelet above 20k;
 - iii. growth factors for neutropenia can be started if ANC is below 1000/µL. Filgrastim is recommended due to a shorter half-life compared with pegfilgrastim.
7. Tocilizumab at the FDA-approved dose for CRS should be administered in the following circumstances:
 - a. grade 3 CRS;
 - b. grade 2 CRS that is not resolving within 72 hours; or
 - grade 2 CRS in the context of other co-morbidities or old age.

8. TOCILIZUMAB SHOULD NOT BE GIVEN FOR ISOLATED NEUROTOXOCITY.
9. If the patient does not respond to tocilizumab within 12 hours, a repeat dose of tocilizumab can be given. If the patient does not respond to the second dose, corticosteroids (i.e. methylprednisolone 1mg/kg every 12 hours) should be prescribed.
10. Patients who are recovering from CRS should not be discharged until they are afebrile for at least 24 hours.
11. If neurotoxicity is suspected, the patient should be evaluated with the Immune Effector Cell Encephalopathy (ICE) scale⁴¹. Patients with Grade 2 neurotoxicity should get a neurology consult and thorough evaluation, e.g., with lumbar puncture and MRI, for other etiologies.
12. Patients who have Descartes-11 related neurotoxicity (except for headache) should receive dexamethasone in the following situations at 10mg/kg every 4-6 hours until symptoms regress to Grade 1:
 - a. grade 3 neurotoxicity lasting for 24 hours;
 - b. grade 4 neurotoxicity; or
 - c. any generalized seizure (in conjunction with other anti-seizure therapies).

Appendix B CELL COLLECTION PROTOCOL FOR THE MANUFACTURING OF DESCARTES PRODUCTS

1 Introduction

1.1 Objective

[REDACTED]

1.2 Background

1.2.1 Chimeric Antigen Receptor (CAR) expressing T-cells

[figure not shown]
Chimeric antigen receptors (CARs) consist of an extra- cellular antigen-recognition domain, which is usually an antibody single-chain variable fragment (scFv), but can also be a peptide or another protein, linked to an intra- cellular signaling domain - usually the CD3 ζ (CD3 zeta) chain of the T-cell receptor. The extracellular portion of the CAR permits the recognition of a specific antigen by a T cell and, subsequently, the signaling domains stimulate T-cell proliferation, cytotoxicity and cytokine secretion to eliminate the target cell. The patients' own T cells (or those from an allogeneic donor) are isolated, activated and genetically modified to generate CAR T cells, which are then infused into the same patient. This approach carries a very low risk of graft-versus- host disease and enables lipid, protein and carbohydrate antigens to be targeted by T cells in an MHC-unrestricted fashion. Additionally, one CAR design can be used to treat all cancers expressing the same antigen.

1.2.2 Descartes-08 and Descartes-11

In order to preserve CAR T-cell efficacy but significantly reduce toxicity, Cartesian Therapeutics pioneered development of anti-BCMA CAR T-cells with defined, controllable pharmacokinetics by transfecting T-cells with CAR mRNA instead of gene transfer. In theory, this key modification should limit uncontrolled expansion and proliferation of circulating CAR T-cells and concomitant toxicities such as CRS and neurotoxicity. The use of mRNA-transfected CAR T-cells is also expected to confer dose-linear pharmacokinetics, that is, the number of circulating CAR T-cells should remain proportional to the number of cells infused. This benefit, which cannot be obtained from permanently modified DNA-transduced CAR T-cells, should provide for more precise dose selection, prevent uncontrolled proliferation, and allow complete clearance of CAR protein to undetectable levels over time. Cartesian is currently testing this hypothesis in a repeat-dose Phase I/II clinical trial of Descartes-08, an anti-BCMA CAR T-cell product with a murine single-chain variable fragment (scFv) and a short (2 d) half-life, in patients with relapsed/refractory MM (NCT 03448978). Notably, unlike for permanently-modified CAR T-cell products, the improved benefit-risk profile of Descartes-08 have allowed its use in an outpatient setting as well as in a non-oncologic indication like myasthenia gravis (NCT04114605). The company developed a follow-up product, Descartes-11, which carries a humanized version of Descartes-08 scFv and also

the half-life of CAR expression on T-cells is increased by 2-3 fold. This product is also being tested in a Phase 1 trial in relapsed refractory multiple myeloma and demonstrates excellent safety similar to its parent product (NCT03994705).

1.2.3 Leukapheresis Procedure

1.3 Rationale

2 Eligibility Criteria

2.1 Inclusion Criteria

1. Patients must have signed written, informed consent.
2. Patients must be 18 years of age or older at the time of enrollment.
3. Patients must have clinical performance status of ECOG 0-2.
4. Patients must be seronegative for HIV.
5. Patients must be seronegative for hepatitis B (HBV) antigen; or, if the patient is positive for the hepatitis B antigen test, he or she must be negative for HBV DNA and must agree to use Hepatitis B prophylaxis as per institution guideline and/or principal investigator discretion.
6. Patients must be seronegative for hepatitis C (HCV) antibody; or, if the hepatitis C antibody test is positive, the patient must be tested for the presence of viremia by RT-PCR and must be HCV RNA negative.
7. Patients must have adequate vital organ function as defined by the following criteria:
 - Bone marrow function defined by absolute neutrophil count (ANC) >1000 cells/mm³ and platelet count $>50,000$ cells/mm³
 - Creatinine Clearance (CrCl) ≥ 30 mL/min or 30 mL/min/1.73 m².
 - Abnormal PT/INR or PTT increased > 1.5 -fold (unless patient is on anticoagulation therapy).

- If the patient is on anticoagulation therapy, there should be no contraindication for holding the drug during the apheresis procedure

8. If the subject is actively on a medication for treatment of an oncologic disease, there should be a minimum of 7 days between the last dose and the leukapheresis procedure. If the agent is a monoclonal antibody then wash-out should be minimum of 21 days and if it is an experimental agent then it should be 5 half-lives.

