2.2 Exclusion Criteria

1. Major chronic illness that is not well managed at the time of study entry and in the opinion of the investigator may increase the risk to the patient.
2. Any other laboratory abnormality that, in the opinion of the investigator, may jeopardize the subject's ability to participate in the study.
3. Any active significant cardiac or pulmonary disease. Note: Patients with asthma and COPD controlled with inhaled medications are allowed.
4. Treatment with any investigational agent within 4 weeks of screening or 5 half-lives of the investigational drug (whichever is longer).
5. History of significant recurrent infections or any active infection at screening visit.
6. Patient is pregnant or lactating.

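### Appendix B's inclusion list gives an abnormal PT/INR or prolonged PTT as part of adequate organ function, so heading and bullet contradict each other

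*Combined protocol and SAP*

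**What the plan says.** Appendix B, Section 2.1 is an inclusion list. Item 7 opens with "Patients must have adequate vital organ function as defined by the following criteria" and has four bullets:

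- minimum neutrophil and platelet counts;
- a minimum creatinine clearance;
- "Abnormal PT/INR or PTT increased > 1.5 -fold (unless patient is on anticoagulation therapy";
- for patients on anticoagulants, "there should be no contraindication for holding the drug during the apheresis procedure".

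Appendix B, Section 2.2 (exclusions) names no clotting test. Its nearest item is exclusion 2: "Any other laboratory abnormality that, in the opinion of the investigator, may jeopardize the subject's ability to participate in the study".

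Appendix B, Section 3.1 has PT/INR and PTT measured at the screening visit, within 28 days of leukapheresis. The main protocol also measures them at baseline (Section 4.1.1), but its eligibility criteria (Sections 2.1.1 and 2.1.2) set no limit on either.

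**The concern.** Three of the four bullets under item 7 state something the patient must satisfy. The clotting bullet states a defect. Placed under that opening sentence, it makes a deranged result part of the definition of adequate function.

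The rule is in active use, because sites will hold PT/INR and PTT results from screening and must judge them against it. Appendix B, Section 3.3.4 lists bleeding and bruising at the venipuncture site among the possible effects of the procedure, so a clotting criterion bears on patient protection. A site that follows the apparent intent departs from the approved text. A site or monitor that follows the text screens in the wrong direction.

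**Working it through.** No arithmetic applies. The check has three parts: apply the bullet to each type of patient, look for text elsewhere that reverses it, and ask how many patients it reaches.

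**1. Applying the bullet.** The second column takes the words under their inclusion heading. The third treats the same words as a bar to collection.

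| Patient | Bullet as an inclusion condition (as written) | Same words as a bar |
|---|---|---|
| No anticoagulant, PT/INR and PTT normal | not met, so item 7 fails | not barred |
| No anticoagulant, PT/INR normal, PTT raised by more than 1.5-fold | met | barred |
| No anticoagulant, PTT normal, PT/INR abnormal but raised by less than 1.5-fold | met if 1.5-fold belongs to PTT only; not met if it belongs to both | barred if 1.5-fold belongs to PTT only; not barred if it belongs to both |
| On an anticoagulant | exempt; the next bullet applies | exempt; the next bullet applies |

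The first two rows show the inversion. The third shows a separate ambiguity: "Abnormal PT/INR or PTT increased" can be read with the 1.5-fold figure attached to PTT alone or to both tests. Changing the direction of the bullet does not settle that.

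The exception, "unless patient is on anticoagulation therapy", gives internal evidence of what was meant. Exempting patients whose clotting is altered by a drug makes sense if altered clotting would otherwise keep a patient out. It makes little sense if altered clotting is what the criterion requires. The bullet therefore looks like exclusion wording placed in an inclusion list.

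**2. Looking for a correction.**

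- Appendix B, Section 2.2: no clotting test or limit, only the discretionary exclusion 2.
- Main protocol Section 2.1.1, item 12 (organ function): marrow, liver, cardiac and renal limits, with no clotting limit.
- Main protocol Section 2.1.2, item 10: prior thromboembolism, recent haemorrhage and whether anticoagulation can be withheld. It gives no PT/INR or PTT limit.
- Main protocol Section 4.1.1 and Appendix B, Section 3.1: the tests are listed without a limit.

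The inverted bullet is thus the only PT/INR or PTT eligibility criterion in the documents. It is a complete phrase with its own figure and its own exception, and nothing suggests that a word was lost to redaction or text extraction.

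**3. Reach.** Main protocol Section 2.2.1 refers a patient to Appendix B when no cells are available at screening. A patient with cells in hand need not pass item 7 to be treated. The documents do not say how many of the planned 34 (main protocol Section 6) will need collection, how many will be on anticoagulants, or how many will have normal clotting. The number who fail the bullet as written could therefore lie anywhere from a few to nearly all of the 34. Appendix B also serves Descartes products more widely (its Section 2.3.1), so its population is not the same as this trial's.

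**The case against.** The strongest reply is that nobody would apply the bullet literally. The opening sentence of item 7 makes the purpose plain, the next bullet deals sensibly with anticoagulants, and Appendix B, Section 3.3 leaves toxicity management to institutional guidelines and the apheresis physician. On this view it is a drafting slip in an appendix, with no effect on any endpoint or analysis. Much of that stands: most sites would probably infer the intent, and actual harm is unlikely. What does not stand is the step from there to leaving the text alone. An eligibility rule applied to real test results should not depend on staff disregarding its wording.

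The reply also rightly limits several stronger readings that a reader might infer.

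- *Patients with prolonged clotting qualify for leukapheresis.* They satisfy one bullet. The platelet minimum and all other criteria still apply, and exclusion 2 lets the investigator keep them out.
- *Nearly all 34 patients fail eligibility.* This is only the upper end of an unknown range, because referral to Appendix B depends on whether cells are already available.
- *Every correctly collected patient is a protocol deviation.* The bullet can be breached in this way only by patients collected under Appendix B who are not on anticoagulation and have normal clotting. Appendix B, Section 4.1.5 also defines a deviation as a single unintentional departure, which fits a systematic wording error poorly.

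**Conclusion.** The bullet is wrong as written: it is an internal contradiction in an eligibility rule. As worded, a patient not on anticoagulation fails item 7 with normal clotting and satisfies that bullet with prolonged clotting.

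The conclusion rests on the text alone, read under its own heading, and on the absence of a correcting statement elsewhere. The number of patients affected cannot be fixed from the documents. The null rate of 10%, the assumed rate of 35%, the sample size of 34 and the Day 28 endpoint do not depend on this bullet. A reader might infer a threat to the trial's results or a demonstrated bleeding hazard, but the documents support neither. The correction is still worth making, because the rule is safety-related and the only one of its kind in the documents.

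**What to change.** The sponsor should reconcile the bullet with the opening sentence of item 7 in Appendix B, Section 2.1. Either of two edits would do so:

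- reword the bullet so that it describes adequate function, in line with its neighbours; or
- move it to the exclusion list in Appendix B, Section 2.2.

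Whichever is chosen, the same edit should say whether the existing 1.5-fold figure applies to PT/INR as well as PTT. Moving the words unchanged would leave that open, and could be read as excluding any abnormal PT/INR. The limit itself is for the sponsor to confirm; none is proposed here.

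The cost is one line in an amendment. No change is needed to the screening tests, the sample size or the analysis.

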2.2 Exclusion Criteria

1. Major chronic illness that is not well managed at the time of study entry and in the opinion of the investigator may increase the risk to the patient.
2. Any other laboratory abnormality that, in the opinion of the investigator, may jeopardize the subject's ability to participate in the study.
3. Any active significant cardiac or pulmonary disease. Note: Patients with asthma and COPD controlled with inhaled medications are allowed.
4. Treatment with any investigational agent within 4 weeks of screening or 5 half-lives of the investigational drug (whichever is longer).
5. History of significant recurrent infections or any active infection at screening visit.
6. Patient is pregnant or lactating.

2.3 Screening, Evaluation and Enrollment

2.3.1 Recruitment of Patients

Subjects who are enrolled into a study using Descartes products will be referred for cell collection.

2.3.2 Screening Evaluation

Please refer to [Section 4.1.1](#) for Screening visit evaluations.

2.3.3 Enrollment

To enroll a subject on this study, the following documents are required:

- Copy of signed/dated consent and HIPAA Authorization
- Source documentation to confirm enrollment/eligibility

3. Study Implementation

3.1 Screening Procedures

Within 28 days of leukapheresis procedure, patients who sign consent will be evaluated at a screening visit for the following procedures:

- Informed consent
- Demographics, medical history
- Concomitant medications
- Vital signs (including pulse oximetry)
- Full physical examination
- PT/INR, PTT
- CBC with differential (should include lymphocyte and neutrophil count, platelet count)
- Serum Chemistry: Glucose, sodium, potassium, chloride, calcium, magnesium, phosphate, BUN, creatinine

The following laboratories should be within 7 days of collection:

- Platelet Count
- Potassium
- Magnesium

The following laboratories should be within 90 days of collection:

- Anti-HIV antibody, anti-Hepatitis B antibody, Hepatitis B antigen, Hepatitis C Antibody
- Lymphocyte subset (should include absolute number and percentages of CD19+, CD4+, CD8+, CD3+, CD16/CD56+ cells in peripheral blood)

